C2.2 Aim 1: Investigate the feasibility of incorporating automatic triggering of the taVNS device using EMG sensors. *Rationale:* Manual taVNS triggering is mentally taxing for a therapist providing intensive CIMT intervention. Movement based, EMG-triggering should decrease the overall burden allowing the therapist to provide high-quality CIMT. Automation may improve pairing of stimulation and motion instead of relying on the therapists to remember to activate/terminate stimulation. It may also decrease the number of personnel required. Using EMG sensors to track every motion would require extensive set-up and complicate treatment by increasing the wires the therapist must manage. Therefore, we aim to use EMG to selectively target key muscle groups.

C2.2.1 Models of pairing stimulation to motor activation Direct pairing of stimulation to movement is most effective for functional outcomes¹⁴. In adult studies therapists manually trigger stimulation for discrete motions that target movement impairments^{13,20}. Infant therapy sessions cannot be setup as a series of discrete movements because infants cannot follow directions, have short attention spans, and are only beginning to develop isolated arm movements. In fact, the kinematic and EMG profiles of young infants' reaching indicate that

Title: Extending taVNS Paired with Infant CIMT into a Home-Based Setting: Technology

Development Requisite for a Randomized Trial

PI: [name]

healthy infants do not show discrete reaching motions indicated by modulation of EMG amplitude until 18 months²⁵. Variability is a key element of infant motor development as infants continually trial new movement pattern combinations as they refine skills and learn to adapt movements to match the demands of new environments²⁶. Infant reaching kinematic profiles instead appear **more similar to continuous motions and multistep movements**²⁷. While this seems like a challenge for automation, it may actually simplify automation, since we want to pair taVNS stimulation with active motor planning and execution of general reaching and dynamic trunk control and do not need to specifically target one motion. *Therefore, we only need to target a few key muscle groups that are consistently activated with immature reaching patterns of young infants.*

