C2.2.2 Targeted Muscle Groups We aim to automate 75% of stimulation time without significantly increasing the burden of system set-up/treatment delivery. We will use 2 sets of EMG sensors placed on the muscle groups activated in the vast majority of reaching and dynamic balance tasks.

- Reaching- Immature reaching in infants is initially driven by the biceps and triceps^{28,29}. As targeted reaching improves there is an increased use of the deltoids and upper trapezius as prime movers. Depending on the age/ability of the child we will target biceps brachii or anterior deltoid^{28,29}.
- Trunk control- EMG literature related to development of dynamic sitting balance indicates that thoracic level paraspinal muscles are most involved with emerging sitting balance and transitions to lumbar paraspinal activation as infants progress to more independent sitting balance²⁸⁻³⁰.

C2.2.3 Outcome measures for EMG automation taVNS stimulation is most effective when directly paired with active movements. Infant movement kinematics are characteristic of continuous movements rather than discrete movements. Since motions are not clearly discrete, we cannot count the number of stimulations and movements. Instead, a second therapist will record the time that the infant is actively engaged in movement tasks and compare that to the total time of taVNS stimulation, recorded by data acquisition modules in our taVNS set-up. One therapist will be delivering CIMT, a second therapist will be recording active movement time. For the first 2 participants, treatments will be completed in the research lab. This will allow the full team to be present, making sure that EMG triggered stimulation is occurring at the same time as active movement (the screen turns green when stimulation is on). If stimulation is not being delivered during active movement, modifications will be made to the system (e.g. changing amplification threshold for triggering, adjusting sensor location, etc). If total stimulation time is within 75% of total active movement time for therapy sessions in the first 2 infants, then we will transition CIMT delivery to the home-based setting for the final 3 infants.

C2.1.2 Treatment Delivery: CIMT-trained therapist with assistance from a research assistant will deliver CIMT for 40 hours (2 hours/day, 5 days/week for 4 weeks) +taVNS delivered via the BabyStrong (BS) system, (Soterix taVNS electric pulse generator unit & Neolead® electrodes).

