- 1) Hydrogel electrodes are placed in front of tragus and inner tragus/cymba chonchae, securing the wires behind head with tape. taVNS unit is attached to the baby using Velcro cummerbund (Fig.1, 2).

Title: Extending taVNS Paired with Infant CIMT into a Home-Based Setting: Technology Development Requisite for a Randomized Trial

PI: [name]

- 2) EMG electrodes will be placed on the shoulder (biceps/deltoid m) and on the trunk (paraspinus m) and connected to the taVNS unit via a wired interface.
- 3) CIMT and BSL therapists establish perceptual threshold (PT) daily, increasing slowly, until infant shows signs of tingling sensation. TaVNS is delivered at $0.1\text{mA} < \text{PT}$, $500\mu\text{sec}$, 25Hz, during each CIMT session, timed with movements of the weaker arm /trunk.
- 4) A CIMT therapist will deliver CIMT and use the manual trigger if needed for hand movements, while a second 'recording' therapist will record the active movement time. The Data Acquisition (DAQ) interface will record the amount of stimulation time and intensity from both EMG and manual triggering.
- 5) Good, moderate or poor impedance is constantly displayed on the taVNS unit. With poor contact, a beep sounds, and the electrode is adjusted.
- 6) Parent and OT will answer weekly questionnaire to assess their perception of ease of use, infant tolerance, and any recommendations for improvement of taVNS system or delivery.

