4.0 Study Endpoints

Primary Research Question: Can taVNS stimulation be automatically triggered during 75% of the total time for active infant arm and trunk movements during CIMT? **Primary Outcome measure:** Percentage of treatment sessions where total stimulation time was 75% of total active movement time.

Limitations and alternative approaches: *Trialing EMG system:* We will trial the EMG sensor system first with two healthy infants in the CHP laboratory setting to trouble shoot set-up and connection issues. The BSL and CIMT team will make any necessary modifications to the EMG-taVNS set-up. *Comparing total movement time to total stimulation time does not ensure stimulation is being provided at the appropriate time:* The stimulation device changes color when stimulation is being provided. Therefore, a second 'recording' therapist can monitor if the screen is green('on') when also recording active movement.

Aim 2: To generate proof of concept evidence demonstrating ability to provide high fidelity CIMT+taVNS treatment in a home-based setting in 3 infants. We will have a second therapist videotape CIMT therapy sessions while the CIMT therapist is delivering taVNS in the home with EMG triggered taVNS. We will randomly score 20% of sessions for CIMT treatment fidelity with published CIMT Fidelity tool. This aim will be completed with the final 3 participants after EMG set-up is finalized with first 2 participants.

Secondary CIMT+taVNS feasibility outcomes: Ability of therapist to operate taVNS easily and successfully by earning a "meet or exceed" score (3 or 4) on random therapy sessions by CIMT Fidelity Instrument. Ability of infant to tolerate wired ear electrode while remaining securely in place during sessions.

Secondary CIMT +taVNS efficacy outcomes: Change in the functional motor outcomes pre and post intervention on the *Quality of Upper Extremity Skills Test (QUEST)*

Title: Extending taVNS Paired with Infant CIMT into a Home-Based Setting: Technology Development Requisite for a Randomized Trial

PI: [name]

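### The 75% ratio does not isolate EMG triggering during arm and trunk movement, so a session can be misclassified in either direction

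*Combined protocol and SAP*

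**What the plan says.** **The question.** Section 4.0 asks: "Can taVNS stimulation be automatically triggered during 75% of the total time for active infant arm and trunk movements during CIMT". Aim 1 in section 1.0 sets the same target, as at least 75%.

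**The denominator.** C2.2.3 says that "a second therapist will record the time that the infant is actively engaged in movement tasks". Its later text says "One therapist will be delivering CIMT, a second therapist will be recording active movement time", and C2.1.2 item 4 says "a second 'recording' therapist will record the active movement time". None of these names a limb or body region, or says when the clock starts and stops.

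**The outcome and the gate.** The primary outcome in section 4.0 is "Percentage of treatment sessions where total stimulation time was 75% of total active movement time". The rule in C2.2.3 for moving the last three infants to home treatment uses the same two totals from the first two infants.

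**The numerator.** C2.2.3 compares movement time with total taVNS stimulation time from the data acquisition (DAQ) modules. C2.1.2 item 4 says that the DAQ records both EMG and manual triggering.

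**What EMG is meant to detect.** Section 3.0 (C2.2) explains that tracking every motion would be too burdensome: "Therefore, we aim to use EMG to selectively target key muscle groups". C2.2.2 provides two sensor sets, one on biceps or anterior deltoid and one on the paraspinals. Stimulation is to be "timed with movements of the weaker arm /trunk" (C2.1.2 item 3). The therapist may "use the manual trigger if needed for hand movements" (item 4), and the general methods in section 3.0 give grasping as an example of behavior left to manual triggering.

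**The concern.** The question is about one thing: how much of the arm and trunk movement is accompanied by stimulation that EMG triggered. The ratio can differ from that at both ends. Time spent only on hand work can count as active movement, which lowers the ratio however well EMG performs. Manual stimulation, and stimulation delivered when the target movement is absent, count in the total, which raises the ratio without any automatic triggering of the target movement.

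The ratio then depends partly on the mix of activities in a session and on how often the therapist presses the trigger. Enrolment covers 6 to 18 months of age and GMFCS levels I to IV, so the mix may well differ between infants, and only two infants decide the gate. Because the timed quantity is undefined, two recording therapists could also time the same session differently. Both the gate and the primary outcome are exposed.

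**Working it through.** **No figure to reproduce.** Section 12.0 says that a power analysis of the primary outcome is not valid with 5 participants. The protocol gives no expected shares for this ratio. The check is therefore ratio arithmetic on assumed values.

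**Inputs**
- Threshold: 75% (C2.2.3 and section 4.0), read as at least 75%, as Aim 1 states it.
- c: share of arm and trunk movement time covered by EMG-triggered stimulation. Assumed.
- h: share of recorded active movement time that is hand-only and does not trigger EMG. Assumed.
- g: share of hand-only time that is manually triggered. Assumed.
- f: off-target stimulation, as a share of recorded time. Assumed.

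**Formula.** Scored ratio R = c(1 − h) + g·h + f. The quantity in the primary question is c alone.

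**1. EMG-triggered time only (g = 0, f = 0), c = 0.85, so on target**
- h = 0.10: 0.85 × 0.90 = 0.765, pass.
- h = 0.20: 0.85 × 0.80 = 0.68, fail.
- h = 0.30: 0.85 × 0.70 = 0.595, fail.

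The coverage needed to pass is c = 0.75/(1 − h). At h = 0.25 this is 0.75/0.75 = 1.00, so beyond that share EMG-triggered time alone cannot reach 75%.

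**2. Adding manual triggering, as the written numerator does.** The manual share that restores 75% is g = (0.75 − c(1 − h))/h. With c = 0.85:
- h = 0.20: (0.75 − 0.68)/0.20 = 0.35.
- h = 0.30: (0.75 − 0.595)/0.30 = 0.52.

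**3. A pass by a system below target.** Take c = 0.60 and h = 0.15, with manual time of 0.10 of recorded time (g = 0.10/0.15 = 0.67) and f = 0.15. Then R = 0.60 × 0.85 + 0.10 + 0.15 = 0.51 + 0.25 = 0.76, a pass with coverage 15 points below target.

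**4. Correcting only the denominator.** Take c = 0.65, h = 0.20, g = 0.50 and f = 0.
- Broad denominator: 0.65 × 0.80 + 0.50 × 0.20 = 0.52 + 0.10 = 0.62, a correct fail.
- Denominator limited to arm and trunk, numerator unchanged: 0.62/0.80 = 0.775, a false pass.

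Off-target time alone can do the same: with h = 0, c = 0.60 and f = 0.15, R = 0.75.

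**5. Correcting both.** With the denominator limited to arm and trunk movement and the numerator limited to EMG-triggered stimulation overlapping it, R = c. Coverage of 0.85 scores 85% and passes; 0.60 scores 60% and fails.

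**The case against.** **A broad denominator may be intended.** The general methods in section 3.0 set the target against all time in active movement and then allow manual triggering for grasping. C2.2.2 speaks of automating 75% of stimulation time. On this reading the remaining 25% is the allowance for movement that EMG misses, and a session with much hand work is a real shortfall. The reading is possible, but it departs from the primary question and Aim 1, which name arm and trunk movement. It also does not rescue the written ratio, because a numerator that includes manual triggering does not measure automation under either reading.

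**Hand-only time may be small.** Section 3.0 describes infant movement as continuous and multistep, and places sensors where most reaching and balance tasks activate muscle. Hand work during reaching or sitting may therefore trigger EMG anyway, and being actively engaged may exclude pauses. This stands: h could be near zero, and the documents give no value.

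**The protocol recognises a limit of comparing totals.** Section 4.0 admits that totals do not show correct timing and has the recording therapist watch for the green screen. That check concerns timing, not which movement is counted, and it does not enter the outcome.

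**Stronger readings that the documents do not support.** A reader might infer that the denominator is definitely task engagement. That phrase is used interchangeably with active movement time, and neither is defined. A reader might infer that the primary question names the weaker arm. It says arm and trunk; the weaker arm comes from C2.1.2 item 3. A reader might also infer that the error only makes good systems fail. That leaves out the manual and off-target stimulation in the written numerator.

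**Conclusion.** The concern holds as a mismatch between the question and the measure. The ratio behind both the home-transition gate and the primary outcome is not limited to arm and trunk movement in its denominator, or to EMG triggering of that movement in its numerator.

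It can misclassify a session in either direction. Under the assumed values, a system with 85% coverage scores between 59.5% and 76.5% on EMG-triggered time as the hand-only share runs from 30% down to 10%, and a system with 60% coverage can score 76%. These figures illustrate what is possible; they are not estimates. They assume that hand-only time does not trigger EMG, and every share is the reviewer's assumption. Neither the size nor the net direction can be found from the documents.

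The change should be made before enrolment: it bears on the primary outcome, costs little now, and is hard to apply once sessions have been timed under an undefined rule.

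**What to change.** 1. In C2.2.3, C2.1.2 item 4 and section 4.0, define active movement time in identical words: visible active movement of the treated (weaker) arm, or dynamic trunk movement, with a rule for starting and stopping the clock.
2. Use as numerator only EMG-triggered stimulation that overlaps that time.
3. Apply this one ratio, with at least 75% as the threshold, to both the home-transition gate and the primary outcome.
4. Time hand-only activity as a separate category and report it beside manually triggered stimulation time.
5. Keep the total-stimulation ratio as a secondary description.

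Items 1 and 2 must go together, since narrowing the denominator alone can create a false pass (working, step 4).

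**Cost.** Protocol wording, one extra category on the timing sheet, and slightly more demanding timing. The timing record must be aligned with the DAQ log, and the log must separate EMG from manual triggers by time; the protocol does not say whether it does. The recording therapist, the DAQ and session video are already planned, and the timing can be completed from video.

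### The 75% ratio of stimulation time to movement time is only an upper limit on EMG coverage: it can show that the primary target was missed, but not that it was met

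*Combined protocol and SAP*

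**What the plan says.** The primary research question in section 4.0 reads "Can taVNS stimulation be automatically triggered during 75% of the total time for active infant arm and trunk movements during CIMT". Section 3.0 (general methods) and section 10.0 tie the move to the home to the same idea: EMG triggering has to deliver stimulation for 75% of the time spent in active movement. Aim 1 in section 1.0 states the 75% as a minimum.

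The measures are built differently.

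- **Measurement (C2.2.3).** The task given to a second therapist is to "record the time that the infant is actively engaged in movement tasks and compare that to the total time of taVNS stimulation".
- **Primary outcome (4.0).** "Percentage of treatment sessions where total stimulation time was 75% of total active movement time".
- **Rule for moving to the home (C2.2.3).** "If total stimulation time is within 75% of total active movement time for therapy sessions in the first 2 infants".
- **Automation aim (C2.2.2).** "We aim to automate 75% of stimulation time", which has stimulation time rather than movement time as its denominator.

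Manual triggering stays available for behaviours such as grasping (3.0, 10.0). Item 4 of C2.1.2 has the data acquisition (DAQ) interface log stimulation from both the EMG and the manual trigger.

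On timing, section 4.0 states the limitation openly: "Comparing total movement time to total stimulation time does not ensure stimulation is being provided at the appropriate time". Its answer is that the recording therapist "can monitor if the screen is green" while timing movement. For the first two infants, C2.2.3 adds that the whole team will be in the lab, "making sure that EMG triggered stimulation is occurring at the same time as active movement", and will adjust the system if it is not.

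**The concern.** The question is about one trigger source and about time that coincides with movement. The ratio of totals keeps neither condition. Stimulation started by hand counts towards it, and so does stimulation delivered while the infant is at rest. Reducing reliance on manual triggering is the reason for Aim 1, so counting manual time towards success works against the aim. The documents do not acknowledge the trigger-source gap.

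The green-screen checks address timing, but they have no threshold, are not stated to be recorded, and feed into neither the outcome nor the rule for moving to the home. As described, a green screen shows that stimulation is on, not which trigger caused it.

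Two things are at stake. First, the numerical rule in C2.2.3 can be satisfied while the coverage threshold in sections 3.0 and 10.0 is not. Second, section 1.0 says the results are to support a grant application for a randomised home-based trial. A high percentage of passing sessions would be read there as evidence that automatic triggering works, which the measure cannot establish.

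**Working it through.** **Inputs from the plan.** C2.1.2 gives 2 hours/day, 5 days/week, 4 weeks. This reproduces the stated exposure: 2 × 5 × 4 = 40 hours, or 20 sessions of 120 minutes per infant, with 40 sessions in the two lab infants and 60 in the three home infants. The 75% is a chosen target with no derivation, and section 12.0 says a power analysis is not valid for five participants, so there is no other figure to reproduce.

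**Inputs not in the plan (assumed, shown as ranges).** a = share of the session spent in active movement; f = share of rest time that is stimulated; m = share of stimulation time that is manual-only, meaning the manual trigger is on and EMG is not.

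**Step 1: what the ratio contains.** Let M be active movement time and R the plan's ratio (total stimulation time / M). Let c be EMG coverage (EMG-triggered time during movement / M). Then

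R = c + (manual-only time during movement)/M + (stimulation time outside movement)/M.

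The last two terms cannot be negative, so c ≤ R. Equality needs both to be zero, and the plan neither requires nor tests this. R < 75% therefore implies c < 75%; R ≥ 75% implies nothing definite about c.

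**Step 2: trigger source, with perfect timing and R = 75%.** Here c = 0.75(1 − m).

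| m | EMG coverage |
|---|---|
| 10% | 67.5% |
| 20% | 60% |
| 25% | 56.25% |

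In minutes for the last row: with 60 minutes of movement, 45 are stimulated, 33.75 by EMG and 11.25 by hand. That row also meets the C2.2.2 automation aim exactly (33.75/45 = 75%). If some stimulation also falls outside movement, coverage is lower, so these are ceilings.

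**Step 3: overlap, with no manual triggering.** Here R = c + f(1 − a)/a. For 60% coverage to score 75%, f = 0.15a/(1 − a).

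| a | rest time that must be stimulated |
|---|---|
| 50% | 15% |
| 70% | 35% |
| 80% | 60% |
| 90% | 135%, impossible |

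In minutes at a = 50%: 36 of 60 movement minutes stimulated, plus 9 of 60 rest minutes, gives 45/60 = 75%.

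**Step 4: why coverage alone is not enough.** A device left on throughout a 120-minute session with 60 minutes of movement has R = 120/60 = 200% and coverage of 100%. It passes any minimum on either measure. The share of EMG-triggered time outside movement has to be reported beside the coverage.

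**The case against.** The strongest reply is that the team saw the timing problem. Section 4.0 states it and assigns someone to watch the screen. In the lab phase the whole team checks concurrence, and corrective changes come before the decision to move to the home. A device driven by muscle activity is unlikely to fire mostly at rest. Manual use is described narrowly, for hand movements if needed, and a press made while EMG is already active adds no manual-only time. The DAQ names both sources, so an EMG-only count may already be obtainable. Aim 1 gives the minimum explicitly, and C2.2.3 can be read as putting the general statements in 3.0 and 10.0 into operation. The study is a five-infant technology pilot.

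Most of this stands and limits the point. A reader might infer that timing was overlooked, or that the checks will go unrecorded. The documents support neither: the limitation is disclosed, and they simply do not say whether the checks are logged. A reader might also infer that the ratio is worthless, but it is informative when it falls below 75%. Finally, the arithmetic permits a coverage of 0% at a 75% score when movement fills half the session. That would need the device to fire only at rest and never during movement, which nothing in the documents suggests. At a movement share of 90% the lower limit is 0.75 − 0.1/0.9 = 64%.

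The reply does not close the gap between question and measure. An available split by source is not used unless the outcome calls for it, and a check outside the outcome cannot support the outcome's conclusion. C2.2.3 notes that movements are not clearly discrete. That explains why they are not counted, but the plan already times movement, so overlap in time can be attempted.

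**Conclusion.** The point holds and should be fixed. As defined, the primary outcome and the rule for moving to the home bound EMG coverage from above and do not measure it. Failing sessions can be interpreted, apart from error in timing movement; passing sessions cannot be taken as meeting the target.

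The possible shortfall is 7.5 to 18.75 percentage points for manual-only shares of 10% to 25%, and 15 points in the overlap example. These are illustrations under assumed shares, not forecasts, because the plan gives neither the movement share nor the manual share. The overlap gap shrinks as movement fills more of the session; the manual gap does not. The existence of the gap depends on no particular value, only on manual-only stimulation or stimulation at rest being possible, and the plan expressly allows the first.

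**What to change.** Reconcile Aim 1 (1.0), the general methods and C2.2.2–C2.2.3 (3.0), section 4.0 and section 10.0 to one definition, used for both the primary outcome and the rule for moving to the home: EMG-triggered stimulation time during active movement, divided by active movement time, at least 75% (the minimum already in Aim 1). Manual triggering is left out of this count only; its use in sessions is unchanged.

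The recording therapist, who already times movement, marks start and stop against the DAQ clock. Report for each session the share of EMG-triggered time outside active movement. Some of that time may be legitimate pairing with motor planning, which C2.2.1 also wants, so it is reported for interpretation and no limit is proposed here.

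Before the first infant, confirm that the DAQ keeps time stamps and trigger source; the documents do not say. Fallbacks:

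- **Overlap cannot be captured:** use EMG-triggered time as the numerator, log the green-screen check already planned, and report the ratio as an upper limit on coverage.
- **Trigger source cannot be separated:** report EMG and manual combined, and make no claim about automatic triggering.

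The cost is rewording plus the start and stop marks. The home workload needs checking: sections 6.0 & 7.0 describe one accompanying team member who assists, films and monitors the infant, while C2.1.2 gives movement timing to a second therapist. Expect a probably less favourable success percentage, and some marking error because movements are not clearly discrete. Second-rater agreement and video scoring are optional extras and not part of this fix.
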